# **7.0 Conduct of the Study**

## **7.1 Visit Schedule**

- 7.1.1 Baseline laboratory must be done within 14 days of study entry.
- 7.1.1 Baseline imaging studies must be done within 4 weeks of study entry.
- 7.1.3 Baseline imaging studies will include computed tomography of chest and abdomen and bone scan (correlating bone X-rays is required if bone scan is positive), or PET scan.
- 7.1.4 Baseline laboratory studies will include a complete blood count, electrolytes, liver functions, tumor markers (CEA and CA 27.29), creatinine.

7.1.5 Laboratory tests: Week 1 2, 3, 4, 6, 8: Complete blood count, liver, electrolytes and creatinin. These laboratory tests will be performed monthly thereafter.

7.1.6 Clinic visits with physical exam: Baseline, months 1, 2, 4, 6, 9, 12 (Tumor markers (CEA and CA 27.29) will be drawn during these visits.

7.1.7 Radiologic imaging/restaging: Months 2, 4, 6, 9, 12 : Affected area will be evaluated. Patients with stable or responsive disease will be followed every 3 months thereafter.

7.1.8 Correlative studies: Serum for angiogenic molecules and cytokines including: serum vascular endothelial growth factor (sVEGF), basic fibroblast growth factor (bFGF), Interleukine-8 (IL-8), platelet-derived growth factor (PDGF), E-selectin, tumor-necrosis factor- $\alpha$  (TNF- $\alpha$ ), tumor-necrosis factor- $\beta$  (TNF- $\beta$ ), IGF-II and IGFBP-3 and proteomic analysis: Baseline and months 2 and 4.

**Table 7 Evaluation and Visit Schedule**

Examination	Prestudy	Week					Month				
		1	2	3	4	6	2	4	6	9	12
Informed consent	X										
Demographics	X										
Medical History	X										
Concurrent Medications	X				X		X	X	X	X	X
Inclusion/exclusion criteria	X										
Vital signs	X				X		X	X	X	X	X
Physical examination	X				X		X	X	X	X	X
Performans Status	X				X		X	X	X	X	X
Body Weight	X				X		X	X	X	X	X
Height	X										
ECG	X										
Laboratory test	X		X	X	X	X	X	X	X	X	X
Imaging studies	X						X	X	X	X	X
Serum markers	X						X	X			
Tissue markers	X						X				

## 8.0 Efficacy Assessment

### 8.1 Definitions

Response and progression will be evaluated in this study using the new international criteria proposed by the Response Evaluation Criteria in Solid Tumors (RECIST) Committee [JNCI 92(3):205-216, 2000]. Changes in only the largest diameter (unidimensional measurement) of the tumor lesions are used in the RECIST criteria. Note: Lesions are either measurable or non-measurable using the criteria provided below. The term "evaluable" in reference to measurability will not be used because it does not provide additional meaning or accuracy

#### 8.1.1 Measurable disease

Measurable lesions are defined as those that can be accurately measured in at least one dimension (longest diameter to be recorded) as  $\geq 10$  mm with conventional techniques (PET, CT, MRI, x-ray) or a with spiral CT scan. All tumor measurements must be recorded in millimeters (or decimal fractions of

centimeters).

#### 8.1.2 Non-measurable disease

All other lesions (or sites of disease), including small lesions (longest diameter <10 mm), are considered non-measurable disease. Bone lesions, leptomeningeal disease, ascites, pleural/pericardial effusions, lymphangitis cutis/pulmonis, inflammatory breast disease, abdominal masses (not followed by CT or MRI), and cystic lesions are all non-measurable.

#### 8.1.3 Target lesions

All measurable lesions up to a maximum of five lesions per organ and 10 lesions in total representative of all involved organs should be identified as target lesions and recorded and measured at baseline. Target lesions should be selected on the basis of their size (lesions with the longest diameter) and their suitability for accurate repeated measurements (either by imaging techniques or clinically). A sum of the longest diameter (LD) for all target lesions will be calculated and reported as the baseline sum LD. The baseline sum LD will be used as reference by which to characterize the objective tumor response.

#### 8.1.4 Non-target lesions

All other lesions (or sites of disease) should be identified as **non-target lesions** and should also be recorded at baseline. Non-target lesions include measurable lesions that exceed the maximum numbers per organ or total of all involved organs as well as non-measurable lesions. Measurements of these lesions are not required, but the presence or absence of each should be noted throughout follow-up.

### 8.2 Guidelines for Evaluation of Measurable Disease

The same method of assessment and the same technique should be used to characterize each identified and reported lesion at baseline and during follow-up. Imaging-based evaluation is preferred to evaluation by clinical examination when both methods have been used to assess the antitumor effect of a treatment.

**Clinical lesions.** Clinical lesions will only be considered measurable when they are superficial (e.g., skin nodules and palpable lymph nodes). In the case of skin lesions, documentation by color photography, including a ruler to estimate the size of the lesion, is recommended.

**Chest x-ray.** Lesions on chest x-ray are acceptable as measurable lesions when they are clearly defined and surrounded by aerated lung. However, CT is preferable.

**Spiral CT and MRI.** For CT, cuts of 7 or 7.5 mm slice thickness (contiguously), for MR 6-10 mm slice thickness should be used. This applies to tumors of the chest, abdomen, and pelvis. Head and neck tumors and those of extremities usually require specific protocols.

**Ultrasound (US).** When the primary endpoint of the study is objective response evaluation, US should not be used to measure tumor lesions. It is, however, a possible alternative to clinical measurements of superficial palpable lymph nodes, subcutaneous lesions, and thyroid nodules. US might also be useful to confirm the complete disappearance of superficial lesions usually assessed by clinical examination.

**Tumor markers.** Tumor markers alone cannot be used to assess response. If markers are initially above the upper normal limit, they must normalize for a patient to be considered in complete clinical response.

### 8.3 Response Definitions:

**Complete Response (CR).** Disappearance of all evidence of tumor for at least one cycle of therapy (four weeks). Bone lesions must have improved by scan and shown complete reossification by x-ray. The patient must be free of all symptoms of cancer. Markers must be normal.

**Partial Response (PR).** 30% or greater decrease in the sum of the products of diameters of all measured lesions persisting for at least one cycle of therapy or 4 weeks. Non-measurable, but evaluable, lesions must decrease by at least 30%. No lesion may increase in size and no new lesion may appear. Bone lesions must have improved by scan and shown some reossification by x-ray. Markers must have improved.

**Minor Response (MR).** A measurable decrease in measurable lesion(s), which is too small or too brief to qualify as a Partial Response. MR is considered a failure, but should be noted as a possible signal of biologic activity.

**Progressive Disease (PD).** Any increase of  $\geq 25\%$  in the sum of the products of diameters of any measurable lesion or in estimated size of non-measurable lesions or appearance of an unequivocally new lesion. Patients should have received at least two cycles of therapy before a designation of progression is made. An increase of 50% or development of unequivocally new lesions between the first and second cycle will be considered progression without repeat measurements.

**No Change (NC).** No change in tumor size, or  $<25\%$  increase in size.

MR and PD are considered failures.

Development of a new brain lesion will be considered progressive disease.

**Confirmation of Response.** To be assigned a status of PR or CR, changes in tumor measurements must be confirmed by repeat assessments that should be performed 4 weeks after the criteria for response are first met. In the case of SD, follow-up measurements must have met the SD criteria at least once after study entry at a minimum interval of 8 weeks.

**Response and Survival Durations.** The survival of patients will be measured from entry into protocol. Duration of response will be measured from first observation of the response until progression of disease.

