### **3.2 Study Population**

### **3.2.1 Inclusion criteria**

1. Postmenopausal women able to comply with the protocol requirements with metastatic breast cancer, whose tumors are estrogen (ER) and/or progesterone (PgR) positive, defined by core biopsy immunohistochemistry with > 10% positive malignant epithelial cells.
2. Patients must have documented expression of either PDGFR or CD117 (c-kit) by immunohistochemistry.
3. Patients may have received tamoxifen in the adjuvant/neoadjuvant setting. Patients may have previously received chemotherapy in the adjuvant/ neoadjuvant setting, though this is not required. Prior chemotherapy for metastatic breast cancer is allowed. Concomitant bisphosphonates are allowed for patients with bone metastases and who have another site of measurable disease.
4. Post menopausal status defined by one of the following :
  - no spontaneous menses for at least 1 year, in women >55 years
  - spontaneous menses within the past 1 year in women ≤ 55 years with postmenopausal gonadotrophin levels (LH and FSH levels >40 IU/L ) or postmenopausal estradiol levels ( <5 ng/dl) or according to the definition of “postmenopausal range” for the laboratory involved
  - bilateral oophorectomy
5. Performance status, ECOG ≤ 2
6. Patients must have measurable disease, defined as at least one lesion that can be accurately measured in at least one dimension (longest diameter to be recorded) as ≥10 mm with conventional techniques. See section 8.2 for the evaluation of measurable disease. Bone disease only will not be accepted as measurable disease. Pleural or peritoneal effusions will not be accepted as measurable disease.
7. Adequate bone marrow function (ANC  $\geq 1.5 \times 10^9/L$  and platelets  $\geq 100.0 \times 10^9/L$ , and hemoglobin  $> 10.0 \text{ g/dL}$ ).
8. Adequate renal function (creatinine less than 1.5 mg/dl) and hepatic function (T. Bilirubin less than 1.5 x normal, AST less than 2.5 x normal)
9. A life expectancy of at least 6 months
10. Localized radiotherapy, which does not influence the signal of evaluable lesion, is allowed prior to the initiation of Imatinib Mesylate. Patients must have recovered from the myelosuppressive effects of previous radiotherapy (at least 2-4 weeks).
11. Ability to understand and the willingness to sign a written informed consent.

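### Section 8.3 scores partial response and progression on products of diameters, while Sections 8.1 and 8.1.3 commit the trial to longest diameters, so the primary response rate has two definitions that do not agree

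*Combined protocol and SAP*

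**What the plan says.** Section 8.1 names the criteria: "Response and progression will be evaluated in this study using the new international criteria" of the RECIST committee. It adds: "Changes in only the largest diameter (unidimensional measurement) of the tumor lesions are used in the RECIST criteria". Section 8.1.3 selects up to five target lesions per organ and ten in total, sums their longest diameters, and states: "The baseline sum LD will be used as reference by which to characterize the objective tumor response".

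Data collection matches that choice. Eligibility (Section 3.2.1) requires "at least one lesion that can be accurately measured in at least one dimension (longest diameter to be recorded", and Section 8.1.1 defines measurable lesions in the same way. No section asks for a second, perpendicular diameter.

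Section 8.3 uses a different scale. PR is a "30% or greater decrease in the sum of the products of diameters of all measured lesions", and progression is an increase of at least 25% "in the sum of the products of diameters of any measurable lesion or in estimated size of non-measurable lesions". Section 8.3 never mentions the sum LD or target lesions.

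The PR definition also sets conditions on non-measurable lesions (a 30% decrease), bone, growth of any lesion, and tumor markers. For non-target lesions, however, Section 8.1.4 says: "Measurements of these lesions are not required, but the presence or absence of each should be noted throughout follow-up".

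Section 13.0 builds both interim looks on the number of objective responses: at least 4 of 15, then at least 8 of 30. It does not say which definition of response applies.

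**The concern.** A sum of products is a two-dimensional quantity and a sum of longest diameters is one-dimensional. The same percentage on the two scales is a different amount of tumor change, so a patient can be a responder under one section and not under the other. Response rate is the first objective in Section 1.0 and the count that stops or continues the trial. With two definitions, that count can depend on which paragraph the assessor follows. Section 8.3 is also the only section with numeric cut-offs, so it is the likely one to be used, although the second diameter it needs is not among the data the plan specifies. Time to progression and duration of response carry the same conflict of scale.

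Two smaller points in the PR definition need clarifying:

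- It requires non-measurable lesions, described as evaluable, to shrink by 30%. Section 8.1 drops that word in reference to measurability, and Section 8.1.4 asks only for presence or absence.
- It requires markers to have improved, without saying what that means when they are normal at baseline. Section 8.2 ties its marker condition for complete response to markers that start elevated.

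**Working it through.** **Inputs.** From Section 13.0: letrozole rate beta(136, 317); prior beta(0.60, 1.40) for the combination; stop if Pr[ORR combination > ORR letrozole + 0.10] < 0.05; looks at 15 and 30 patients. From Section 8.3: 30% for PR and 25% for progression, both on products. The documents give no numeric cut-off on the sum LD. **Assumption:** the 30% of Section 8.3 is carried over to the sum LD.

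**1. The plan's own figures.** With x responders in n patients, the combination rate is beta(0.60 + x, 1.40 + n − x). Integrating over beta(136, 317) gives:

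| Responses | Posterior probability | Decision |
|---|---|---|
| 3/15 | 0.043 | stop |
| 4/15 | 0.122 | continue |
| 7/30 | 0.026 | stop |
| 8/30 | 0.059 | continue |

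The stated boundaries of 4 and 8 are therefore right. The exact probability of early termination is P(X ≤ 3) + Σ P(X = x)·P(Y ≤ 7 − x) for x = 4 to 7, where X and Y are the responses in the first and second 15 patients.

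| True ORR | .20 | .30 | .35 | .40 | .45 | .50 |
|---|---|---|---|---|---|---|
| Plan | .83 | .40 | .22 | .11 | .05 | .02 |
| Exact | .819 | .393 | .220 | .108 | .048 | .019 |

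The design arithmetic reproduces to within about 0.01. The fault is in what counts as a response.

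**2. One scale against the other, single lesion or uniform shrinkage.** Let the LD fall by a fraction x and the perpendicular diameter by kx. The product rule is met when (1 − x)(1 − kx) ≤ 0.70.

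- k = 1 (proportional): x = 1 − √0.70 = 16.3%.
- k = 0.5: 0.5x² − 1.5x + 0.30 = 0, so x = 21.6%.
- k = 0 (only the LD shrinks): x = 30%.

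Conversely, a proportional 30% fall in LD is a 1 − 0.70² = 51% fall in product. For progression, a 25% rise in product is a √1.25 − 1 = 11.8% rise in LD under proportional growth.

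**3. Disagreement in both directions (constructed patients, size criterion only).**

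- Patient A: one lesion goes from 40×30 to 33×25 mm. Product 1200 to 825, a fall of 31.3%: meets the product rule. LD 40 to 33, a fall of 17.5%: does not meet 30% on the LD.
- Patient B: one 60×60 mm lesion is unchanged and four 15×15 mm lesions vanish. Sum LD 60 + 4×15 = 120 to 60, a fall of 50%: meets 30% on the LD. Sum of products 3600 + 4×225 = 4500 to 3600, a fall of 20%: does not meet the product rule.

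**4. Reach into the first look.** One reclassified patient changes the decision if the count moves from 3 up to 4 or from 4 down to 3. By the binomial, P(exactly 3 of 15) and P(exactly 4 of 15) are 0.17 and 0.22 at a true rate of .30, and 0.06 and 0.13 at .40.

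**The case against.** The strongest reply is that the documents hold only one numeric rule, the one in Section 8.3. Sections 8.1 and 8.1.3 give a basis and a citation but no percentage, so the second definition needs a figure supplied by the reader. Moreover, if only longest diameters are recorded, the product rule cannot be computed, and Section 8.3 looks like a drafting slip rather than a live competing rule. The example patients are constructed, Patient B is extreme, no shift in response rate is estimated, and a single patient matters only when the count is at the boundary.

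Some of this stands. The size of the disagreement rests on the stated assumption, and the boundary must be close for one patient to decide a look. The net direction is unknown: the product rule is looser for one lesion or uniform shrinkage, it can be stricter with unequal lesions, and the other PR conditions in Section 8.3 make response harder to reach.

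The conflict of basis needs no assumption, however. The 30% is the plan's own PR percentage, placed on the plan's own declared scale. A primary-endpoint rule that cannot be computed from the specified data is an error to correct even if it began as a slip.

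Two further objections are fair and are taken up in the fix: the documents do not say which criteria produced the 136/453 benchmark, and a change of wording still needs the approvals in Section 12.1.

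**Conclusion.** The concern holds and must be fixed before any response is scored. Sections 8.1 and 8.1.3 put response on the sum of longest diameters, Section 8.3 puts it on products of diameters, and nothing reconciles them. On the assumption that 30% applies on both scales, the LD fall that satisfies the product rule for a single lesion lies between 16.3% and 30% as k goes from 1 to 0, and with several unequal lesions the disagreement can reverse. No shift in the response rate is claimed, because the documents give no distribution of tumor change. The stopping boundaries and the early-termination table take the response rate as given and remain correct. What is undefined is which patients count toward it. The two smaller points on non-measurable lesions and markers are clarifications and would not by themselves require an amendment.

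**What to change.** - Restate the PR size criterion in Section 8.3 as at least a 30% decrease in the sum LD of target lesions from the baseline sum LD, consistent with Sections 8.1 and 8.1.3.
- Align the PR condition for non-target lesions with the presence-or-absence recording in Section 8.1.4, including the ban on growth of any lesion, which such recording cannot show.
- State how the PR marker condition applies when baseline markers are normal, in line with Section 8.2.
- Reconcile the progression definition in Section 8.3 with Sections 8.1 and 8.1.3. No cut-off is proposed here, because progression also ends treatment (Sections 5.3 and 11.0).
- Say in Section 13.0 that ORR uses the reconciled definition, and whether the 136/453 benchmark was scored on the same basis.

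The cost is a written amendment with the approvals in Section 12.1: the supporting company and the investigator, and the IRB if the change is judged to affect scientific quality significantly. Longest diameters are already recorded, so no scans or patients are added and the boundaries stay as they are. Compared with scoring on products, the number of patients meeting the PR size criterion may fall (as with Patient A) or rise (as with Patient B).

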## Protocol Body

### 1.0 Objectives

1. To determine the efficacy of Letrozole plus Imatinib Mesylate in patients with ER and or PgR positive metastatic breast cancer. Efficacy will be measured by the rate of clinical tumor response.
2. To determine the safety and tolerability of Letrozole plus Imatinib Mesylate in patients with metastatic breast cancer.
3. To determine the time to disease progression and overall survival in patients with metastatic breast cancer who are treated with Letrozole plus Imatinib Mesylate.

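### When target lesions meet the PR threshold but non-target lesions persist, the data that section 8.1.4 requires cannot show whether the patient is a partial responder

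*Combined protocol and SAP*

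**What the plan says.** Section 1.0 makes response the efficacy measure: "Efficacy will be measured by the rate of clinical tumor response".

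The recording rule is in 8.1.4. It defines the class broadly ("Non-target lesions include measurable lesions that exceed the maximum numbers per organ or total of all involved organs as well as non-measurable lesions") and asks for little: "Measurements of these lesions are not required, but the presence or absence of each should be noted throughout follow-up". Section 8.1.2 places these among the non-measurable sites, which are therefore always non-target: "Bone lesions, leptomeningeal disease, ascites, pleural/pericardial effusions, lymphangitis cutis/pulmonis, inflammatory breast disease".

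The response rule is in 8.3. For PR it says: "Non-measurable, but evaluable, lesions must decrease by at least 30%. No lesion may increase in size and no new lesion may appear". It adds for bone and markers: "Bone lesions must have improved by scan and shown some reossification by x-ray. Markers must have improved". The progression (PD) rule in 8.3 also refers to an increase of 25% or more in the estimated size of non-measurable lesions.

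Section 8.1 says that the term 'evaluable' "in reference to measurability will not be used because it does not provide additional meaning or accuracy".

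On imaging, 7.1.3 asks at baseline for CT with a bone scan (plus correlating x-rays if the scan is positive), or for PET. Section 7.1.7 re-images the affected area at months 2, 4, 6, 9 and 12. Table 7 has one imaging row and names no modality. Inclusion criterion 3 (section 3.2.1) anticipates patients who have bone metastases and another measurable site.

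Section 13.0 continues accrual only with at least 4 responses in 15 patients and then at least 8 in 30. It counts patients removed from the trial as failures.

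**The concern.** Section 8.3 asks quantitative questions about lesions for which 8.1.4 requires a yes/no record. No section says how a 30% change in an effusion, in lymphangitis or in another non-measurable site is to be judged, or where the judgement is written down. Section 13.0 has no rule for a patient still on trial whose PR status cannot be determined.

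Two assessors could therefore classify the same patient differently, each with support in the text. One, following 8.3 literally, would withhold PR because the decrease is not documented. The other, following 8.1 and 8.1.4, would treat the non-target conditions as inoperative and call PR. With boundaries of 4/15 and 8/30, a few such calls can decide whether the trial continues.

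**Working it through.** **1. What the required record can decide**

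| Situation | PR status from the data required |
|---|---|
| Target shrinkage below the PR threshold | Decidable: not PR |
| New lesion | Decidable: not PR |
| A target lesion has grown | Decidable: not PR (target lesions are measured) |
| Target threshold met, all non-target lesions absent | Non-target size conditions met (100% decrease) |
| Target threshold met, non-target lesion present, no new lesion | Not decidable |

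In the last row, 'present' fits a non-measurable lesion that is 40% smaller (size conditions met), unchanged (not PR) or 30% larger (past the 25% PD limit). For measurable lesions beyond the cap of five per organ or ten in total, the 30% condition does not apply on its terms. The no-growth condition does, and presence/absence cannot show it.

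**2. Bone**

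Bone has its own clause, which rests on scan and x-ray and not on 8.1.4. The gap here is in scheduling. The baseline PET option carries no x-ray requirement, and neither 7.1.7 nor Table 7 names follow-up bone x-rays.

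**3. The plan's own design figures**

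Inputs from 13.0: letrozole beta(136, 317), experimental prior beta(0.60, 1.40), margin 0.10, stop if the probability is below 0.05.

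- Posterior probability that ORR exceeds letrozole by more than 0.10: 3/15 gives 0.043 (stop), 4/15 gives 0.122 (continue), 7/30 gives 0.026 (stop), 8/30 gives 0.059 (continue). The boundaries are confirmed.
- Early termination = P(X15 ≤ 3) + P(X15 ≥ 4 and X30 ≤ 7), exact binomial. At true ORR .20/.30/.35/.40/.45/.50 this gives .819/.394/.220/.108/.048/.019, against the stated .83/.40/.22/.11/.05/.02.

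The design figures are sound. The open question is what counts as a response.

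**4. Illustration A: undocumented responses counted as failures**

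The documents give neither the share of patients with non-target disease (f) nor the share of their responses that would be lost (b). Both are assumed. The formula also assumes that responders have non-target disease as often as non-responders.

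Measured ORR = 0.40 × (1 − f × b), put through the stopping rule in step 3:

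| f | b | Measured ORR | Early termination |
|---|---|---|---|
| 0.3 | 0.10 | 0.388 | 0.13 |
| 0.7 | 0.10 | 0.372 | 0.16 |
| 0.3 | 0.25 | 0.370 | 0.17 |
| 0.5 | 0.50 | 0.300 | 0.39 |
| 0.7 | 0.50 | 0.260 | 0.57 |

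The reference at ORR 0.40 is 0.108 (stated .11).

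**5. Illustration B: non-target conditions ignored**

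Suppose ORR under a literal 8.3 is 0.30, and a share L of the responses called would fail the literal rule. Apparent ORR = 0.30 / (1 − L). For L = 0.10, 0.20, 0.30 this is 0.333, 0.375, 0.429. Early termination falls from 0.39 to 0.27, 0.16, 0.07.

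**The case against.** **Measurement is not barred.** Section 8.1.4 says only that it is not required. The affected area is re-imaged, and the PD rule presupposes size estimates, so the images may hold the information. This stands, but it does not close the gap: no method and no required record are defined, so any call would be ad hoc.

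**Strict is not the same as unassessable.** A reader might infer that PR cannot be adjudicated in any patient with non-target disease. The documents do not support that, as the table in step 1 shows. Bone disease seen to be unchanged on scan and x-ray is adjudicable as not PR. So is a patient with a small increase in one target lesion: that is an added condition alongside the sum in 8.1.3, not a contradiction of it. Whether those conditions are too strict is a matter of preference.

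**Direction.** A reader might also infer that ORR is biased downward. That is not established. Assessors who set aside the unrecorded conditions raise ORR relative to literal 8.3. In addition, the documents do not give the response criteria behind the 136/453 letrozole rate, so a disadvantage against that comparator cannot be shown.

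**Size.** The loss rate has no source in the documents and drives Illustration A. At 10% lost, early termination is only 0.13-0.16. The case in which a 40% regimen is stopped as often as one at 30% (0.39) is one assumed combination, not an estimate. This objection stands in full.

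**Conclusion.** The point holds for one group: patients whose target lesions meet the PR threshold while non-target lesions persist and no new lesion appears. For them the data required by 8.1.4 do not determine PR under 8.3, and 8.3 relies on a term that 8.1 sets aside. For bone, the x-ray evidence that 8.3 needs is not explicitly scheduled.

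ORR can be wrong in either direction. On the assumed ranges (f 30-70%, b 10-50%), a true ORR of 40% is measured as 26-39%, with early termination 0.13-0.57 against the stated 0.11. In the opposite direction, a literal ORR of 30% could read as 33-43%. These figures show that the boundaries are sensitive to the ambiguity; they do not predict its effect. The contradiction itself rests on the text alone and needs no assumption. Because it concerns the primary endpoint and both interim decisions, it should be resolved before the first interim analysis.

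**What to change.** Reconcile 8.1.4 and 8.3 so that the non-target parts of both PR and PD use what is recorded. There are two ways:

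- **Qualitative.** PR = target criterion met on the sum, no unequivocal progression of non-target lesions (including bone), and no new lesion. Word non-target PD in the same terms.
- **Quantitative.** Keep size conditions, but require a non-target size assessment, define its method and timing, and give it a place on the case report form. For bone, name the follow-up x-rays and say what applies after a PET baseline.

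Under either option:

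- remove 'evaluable' from 8.3;
- leave the PR marker condition as it is unless it is changed explicitly;
- state in 13.0 how a patient on trial with undeterminable PR counts in ORR and at each interim look.

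Progression also ends treatment (5.3, 11.1), so the investigators should confirm that any new PD wording is acceptable for that use.

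Cost: the qualitative option is a wording change with no added imaging, but PR becomes easier to reach than under a literal 8.3. The quantitative option keeps the stricter endpoint at the price of extra assessment and recording.
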